### B. Background and Significance

Briefly give the background to the present proposal, critically evaluate existing knowledge, and specifically identify the gaps which the project is intended to fill. Cite literature and include a list of references.

Bladder Spasms are a frequent cause of discomfort in the post-operative setting after lithotripsy, and while B and O suppositories are occasionally used post-operatively to relieve bladder spasms, there are no studies that show how effective they are. There are two studies that evaluated the use of B and O suppositories in a perioperative setting after robotic prostatectomies:

Lukasewycz S, Holman M, Kozlowski P, Porter CR, Odom E, Bernards C, Neil N, Corman JM. Does a perioperative belladonna and opium suppository improve postoperative pain following robotic assisted laparoscopic radical prostatectomy?

Results of a single institution randomized study. *Can J Urol.* 2010 Oct;17(5):5377-82. PubMed PMID: 20974030

These two studies show a possible benefit to perioperative belladonna and opium suppositories. However, these studies have never evaluated the use of the suppositories in lithotripsy procedures where the bladder is dilated and drained multiple times during a procedure. The constant distension leads to bladder spasms in the post-operative setting, which require narcotics and anti-muscarinics. There are also no studies to evaluate the effect of timing of administration of these suppositories in lithotripsy cases on postoperative pain, the use of narcotics in the post-operative period, and length of hospital stay.

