#### D. Research Design and Methods

Describe the research design and the procedures to be used to accomplish the specific aims of the project. Include the means by which the data will be collected, analyzed, and interpreted.

-1. Subjects will be identified as meeting inclusion criteria for this study during an office visit at the MFA urology clinic. Opportunity to participate in the study will be offered to the subject and informed consent obtained as appropriate. As noted above, patients will be informed of their right to not participate in the study. Ureteroscopy will still be offered to all patients who meet the appropriate indications, regardless of their participation in this study. Patients will be given a pre-operative survey to determine the severity of any bladder spasms they are

experiencing before surgery and to gauge their level of narcotic usage in the acute setting pre-operatively.

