-2. The patients will be divided into three research arms. Patients will be randomly selected for one of the groups using a random number generator between 1 and 3. There will be a "Control Group" which will receive a rectal exam while still in the operating room in the lithotomy position after the procedure. There will be a "Postoperative OR" group which will receive a B and O suppository while still in the operating room in the lithotomy position after the procedure. Finally, there will be a "Preoperative OR" group which will receive a B and O suppository after the induction of anesthesia prior to beginning the urologic procedure in the lithotomy position. The "Control Group" will receive a rectal exam in the operating room after the procedure but before extubation to simulate the effects of suppository administration so that we know that any effects are due to the medication and not to the placement of the suppository itself. Those patients in the "control group" may receive a B and O suppository as part of standard procedure in the post-operative period if these individuals experience any bladder spasms and wish to have this as a treatment. This administration will be at the discretion of the operating surgeon as it is in standard cases. Patients may also receive Ditropan in the post-operative setting, which is part of the standard procedure for treating bladder spasms following urologic procedures. Patients in the postoperative and preoperative OR groups will be offered Ditropan for any bladder spasms in the post-operative setting to control symptoms, which is part of the normal standard of care for anyone who has already received a B and O suppository with inadequate control of symptoms. All patients will be treated with a normal post-operative pain regimen which may include narcotics. This will be at the discretion of the treating physician.

-3. In the post-operative setting, all subjects will be given a quick survey within 24 hours to assess their amount of discomfort related to bladder spasms/urinary discomfort. In addition, subjects medical charts will be reviewed to determine the amount of antimuscarinics that the patient received 24 hours post-operatively and the amount of narcotic and non-narcotic pain medication that subjects required. Patients not in the experimental arm will be given oral anti-muscarinics to treat any bladder spasms that they may have, but will not be given suppositories.

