-4. Data will be entered into the database following the procedure as available.

-5. Subjects will have clinically appropriate follow-up per the attending urologist. If, as part of that follow-up, clinically relevant events occur, the corresponding data will be recorded in the database.

Note that, with the exception of which particular study arm the subjects are enrolled into and the recording of data as detailed above and below, there will be absolutely

no difference in the care received by patients choosing to participate in this study and those who elect not to participate.

Data will be analyzed using commercially available statistical software. T-tests will be performed for continuous variables and Pearson's Chi-squared tests for categorical variables. Analysis will be tailored to compare B and O Supprenettes Suppositories and placebo/no suppository in order to best answer the research question.

1. Describe any new methodology and its advantage over existing methodologies.

There are no methodologies in this protocol which are new.

2. Discuss potential difficulties and limitations of the proposed procedures and alternative approaches to achieve the aims.

The procedure is designed so that patients receive a B and O suppository as they would as part of standard protocol in the post-operative period if bladder spasms were experienced. The only difference is regarding timing of administration. Therefore, there are no potential difficulties or limitations of the proposed procedure since B and O administration is already a well-accepted treatment for bladder spasms following urologic procedures.

3. Provide a tentative sequence or time table for the study.

November 2015 - IRB approval and begin recruiting patients for study

December 2015 - June 2016 Conducting study according to aforementioned protocol

July 2016 - Begin data analysis and manuscript preparation

4. Specify procedures, situations, or materials that may be hazardous to personnel and the precautions to be taken to ensure safety.

None

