5. Provide justification of the sampling procedure and sample size. Gender and Minority Inclusion, it is required that all research involving human subjects and human materials include minorities and women, as well as males and females of all ages. If one gender and/or minorities are excluded or are inadequately represented in a protocol, particularly in proposed population-based studies, a clear compelling rationale for exclusion or inadequate representation should be provided. The composition of the study population must be described in terms of gender and

racial/ethnic group, together with a rationale for its choice (by age distribution, risk factors, incidence/prevalence, etc.)

All participants undergoing lithotripsy procedures at GW hospital with the included physicians will be asked to participate in the study.

We determined the expected effect sizes based on previous studies of this same treatment in patients who received robot-assisted laparoscopic surgery for prostate CA.

Based on morphine equivalent dose in both Scavonetto, Lamborn, McCaffrey et al. (Can J. Urol 2013) and Lukaswycz, Holman, Kozlowski et al. (Can J Urol 2010), we would like to detect a 4 mg eq. difference between groups, with an expected standard deviation (sd) of 5, i.e., an effect size (d) of 0.8. For post-op pain rated on a 10-point scale both of the previous studies found sd ~2.0. We would like to detect a 1-point difference, so will power for an effect size of 0.5. Scavonetto et al. found approximately 20% of patients required use of rescue B&O suppositories and 60% requiring Oxybutynin for post-op bladder spasm. Thus, for this outcome we will try to detect a difference in percent positive of 20%. For all comparisons, we will use 2-tailed tests with alpha=.05.

Immediate post-op morphine equivalent dose.

In order to have power >.80 to detect an effect size of 0.8 in morphine eq. dose, we would need n=26 per group, or total N=51. For power >.90, we would need 34 per group or total N=68.

Post-op pain.

For an effect size of 0.5, in order to have power >.80, we would need 64 per group, or total N=128. For power >.90, we would need 86 per group, or total N=172.

Use of medication for bladder spasms.

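### Pre-operative spasm severity and narcotic use are collected but not used in the analysis; prespecified ANCOVA would use them at almost no cost, for a gain that may be small

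*Combined protocol and SAP*

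**What the plan says.** Section D, item 1 collects two baseline measures: "Patients will be given a pre-operative survey to determine the severity of any bladder spasms", and, in the same survey, questions to "gauge their level of narcotic usage in the acute setting pre-operatively". Item 3 then measures a related outcome after surgery: "all subjects will be given a quick survey within 24 hours to assess their amount of discomfort related to bladder spasms/urinary discomfort".

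The analysis paragraph of Section D states "T-tests will be performed for continuous variables" and gives Pearson's chi-squared test for categorical variables. It adds "Analysis will be tailored to compare B and O Supprenettes Suppositories and placebo/no suppository", which concerns the groups to be compared, not adjustment. Nowhere does the plan name a covariate, adjusted model, change score, stratum or subgroup that would use the baseline survey.

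The sample-size justification (Section D, question 5) works from unadjusted SDs: 5 mg for morphine-equivalent dose and, for pain, "For post-op pain rated on a 10-point scale both of the previous studies found sd ~2.0". It gives no baseline-outcome correlation. The questionnaires belong to the appendix and are not in the text, so their scales are unknown here. No baseline pain score is described.

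**The concern.** In a randomised comparison, outcome variance that a baseline measure explains can be removed from the error term. An unadjusted t-test leaves it in, so the confidence intervals are wider than the collected data require.

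This matters most if each active arm is compared with control. The plan asks for 64 per group to give pain power above 0.80, but "The patients will be divided into three research arms", and 180 patients split three ways gives 60 per arm. A modest amount of explained variance could restore the target for pain without another patient. Naming the adjustment in advance also prevents a choice of covariates after the data are seen.

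**Working it through.** **Inputs from Section D, question 5:** two-sided alpha 0.05; pain difference 1 point, SD 2 (d = 0.5); morphine-equivalent difference 4 mg, SD 5 (d = 0.8); total 180. **Assumption:** r from 0.1 to 0.5.

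**The plan's own figures reproduce.** The two-sample t-test gives 64 and 86 per group for d = 0.5 (power 0.80 and 0.90), and 26 and 34 for d = 0.8. For 20% v 40%, the pooled normal approximation without continuity correction gives 82.

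**Which comparison.** The text allows three readings: pairwise between three arms (180/3 = 60 v 60), both active arms pooled against control (120 v 60), or two equal groups as in the closing sentence of the sample-size section (90 v 90).

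**Power with ANCOVA.** The residual SD is SD × √(1 − r²), so effective d = 0.5/√(1 − r²). This goes into the noncentral t with one degree of freedom lost. Example at r = 0.3, 60 v 60: d = 0.5/√0.91 = 0.524; noncentrality = 0.524 × √(60 × 60/120) = 2.87; power 0.8125.

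| Pain power | Unadjusted | r = 0.1 | 0.2 | 0.3 | 0.4 | 0.5 |
|---|---|---|---|---|---|---|
| 60 v 60 | 0.775 | 0.779 | 0.792 | 0.813 | 0.842 | 0.880 |
| 120 v 60 | 0.882 | 0.885 | 0.894 | 0.909 | 0.929 | 0.953 |
| 90 v 90 | 0.916 | 0.918 | 0.926 | 0.938 | 0.954 | 0.971 |

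At 60 v 60, power reaches 0.80 at r = 0.245.

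**95% CI half-width** = t × SD × √[(1 − r²)(1/n₁ + 1/n₂)].

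| Half-width, unadjusted, then r = 0.1 to 0.5 | Pain (points) | Morphine equivalents (mg) |
|---|---|---|
| 60 v 60 | 0.72, then 0.72 to 0.63 | 1.81, then 1.80 to 1.57 |
| 120 v 60 | 0.62, then 0.62 to 0.54 | 1.56, then 1.55 to 1.35 |
| 90 v 90 | 0.59, then 0.59 to 0.51 | 1.47, then 1.46 to 1.27 |

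Unadjusted power for morphine-equivalent dose at 60 v 60 is already 0.99, so only the interval improves there.

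**Equivalent sample size** = 180/(1 − r²): about 182, 188, 198 and 240 at r = 0.1, 0.2, 0.3 and 0.5.

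**The formula is slightly optimistic at low r.** It ignores chance covariate imbalance, which inflates variance by about 1 + 1/(N − 4). Setting (1 − r²)(1 + 1/(N − 4)) = 1 gives r² = 1/(N − 3). The break-even r is therefore √(1/117) = 0.092 at N = 120 and √(1/177) = 0.075 at N = 180.

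**Simulation:** 10,000 trials at 60 v 60, 1-point difference, SD 2. The baseline is skewed by assumption: 60% with no spasm, the rest uniform from 1 to 10. The last column has 10% of baselines missing and replaced by the overall mean.

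| r | t-test | ANCOVA | ANCOVA, 10% missing |
|---|---|---|---|
| 0 | 0.773 | 0.770 | 0.770 |
| 0.1 | 0.777 | 0.774 | 0.774 |
| 0.2 | 0.784 | 0.793 | 0.791 |
| 0.3 | 0.773 | 0.811 | 0.807 |
| 0.5 | 0.776 | 0.878 | 0.870 |

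The Monte Carlo standard error is about 0.004. Type I error at r = 0.3 was 0.050, 0.049 and 0.049.

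**The case against.** The strongest case against is that this is a preference whose benefit rests on an unknown r, and that the documents point to a low one. Section B says of lithotripsy "The constant distension leads to bladder spasms in the post-operative setting", so spasm before surgery may say little about spasm after it. Section E excludes chronic pain, chronic analgesic use and prior antimuscarinic use, which probably narrows the baseline range. This stands, and the upper end of the r range should not be read as the expected benefit.

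Survey timing may weaken r further. The survey is described at the clinic visit, but Section F allows consent weeks ahead, in the emergency room or just before surgery, so some baselines may be early or absent. With a fraction m missing and mean-imputed, the effective r² is about (1 − m)r². At r = 0.3 and 60 v 60, pain power falls from 0.813 to 0.801 with 30% missing and to 0.794 with 50% missing. The r of about 0.25 needed for 0.80 therefore presumes complete baselines. This shrinks the gain but does not reverse it.

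The scales are unknown, so the covariates may turn out to be ordinal or yes/no. Any numerical coding keeps ANCOVA valid under randomisation, but the coding must be stated, and entering a covariate as categories would cost more than one degree of freedom.

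Adjustment also does little for spasm medication, the outcome with the largest requirement (82 per group for power above 0.80). Its power at 60 v 60 is about 0.67, and its test is left unchanged. Finally, the spasm/urinary-discomfort score is the closest match to the baseline survey, but the documents give no SD for it and do not say whether it is the same item as the 10-point pain rating. No gain can be computed for it.

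**Conclusion.** The point holds as an optional improvement. Two baseline measures are collected and the stated analysis uses neither. The unadjusted tests remain valid. At 60 v 60, on the plan's own pain inputs, ANCOVA gives no practical gain at r = 0.1, about one percentage point at 0.2, about four at 0.3 and about ten at 0.5. On the 120 v 60 and 90 v 90 readings, and for morphine-equivalent dose, the gain is mainly a narrower interval.

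All of this assumes a value of r that the documents do not supply, and spasm severity is a related covariate for pain, not the same measure. Adjustment does not repair the separate problem of a two-group sample size spread over three arms.

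**What to change.** In the analysis paragraph of Section D, replace the t-tests for continuous outcomes with prespecified ANCOVA, as three separate models:

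1. Post-operative spasm/urinary-discomfort score on arm plus pre-operative spasm severity.
2. 10-point pain score on arm plus pre-operative spasm severity. If this is the same survey item as in model 1, the two become one model.
3. Morphine-equivalent dose on arm plus pre-operative narcotic use.

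State how each covariate is coded and which contrast is tested. Replace a missing baseline value with the overall mean, ignoring arm, so that no randomised patient is dropped. Report the unadjusted differences as well. The chi-squared test for spasm medication can stay; adjusting it is optional, with little expected gain.

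The cost is analysis wording: no new data and no change to the survey schedule. Each model loses one degree of freedom with a single numerical covariate. If r is zero, power for pain at 60 v 60 falls by less than half a percentage point (formula 0.7753 to 0.7752; simulated 0.773 to 0.770).

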## RESEARCH PLAN

### A. Specific Aims

List the broad, long-term objectives and describe concisely and realistically what the specific research described in your proposal is intended to accomplish, and the hypothesis to be tested.

The long-term objectives of the study are to determine whether earlier administration of Belladonna and opium (B and O) suppositories ameliorates the discomfort associated with bladder spasms and reduces the need for oral narcotics and antimuscarinics in the post-operative setting.

Most patients who receive B and O suppositories in the post-operative period receive them in the PACU after expressing discomfort. The administration of B and O suppositories in these cases can often be hours from surgery end time.

The hypothesis to be tested is that giving patients B and O suppositories prior to surgery or post-operatively while still in the operating room will reduce the amount of pain medications that people will need post-operatively, reduce the amount of discomfort that patients experience from bladder spasms, and possibly reduce the length of hospital stay.

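### The stated comparison, B and O against placebo or no suppository, matches no randomised arm and leaves room for grouping by receipt, which would select controls on the outcome

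*Combined protocol and SAP*

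**What the plan says.** **Arms (section D, item 2).** "The patients will be divided into three research arms": a Control Group, a Postoperative OR group and a Preoperative OR group. The Control Group "will receive a rectal exam in the operating room after the procedure but before extubation to simulate the effects of suppository administration". No arm is given a placebo suppository.

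**Later B and O in controls (section D, item 2).** Controls "may receive a B and O suppository as part of standard procedure in the post-operative period if these individuals experience any bladder spasms", provided the patient wants it. The decision lies with the treating side: "This administration will be at the discretion of the operating surgeon as it is in standard cases".

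**A conflicting statement (section D, item 3).** Patients not in the experimental arm are to have oral antimuscarinics for spasms, "but will not be given suppositories".

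**Comparison (section D, data-analysis paragraph).** "Analysis will be tailored to compare B and O Supprenettes Suppositories and placebo/no suppository". The paragraph specifies t-tests for continuous and Pearson chi-squared tests for categorical variables.

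**Sample size (section D, question 5).** This text speaks of treatment and control groups with equal randomisation. It assumes that 20% of treated and 40% of control patients need medication for spasm.

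**Aim (section A).** The trial is to determine "whether earlier administration of Belladonna and opium (B and O) suppositories ameliorates the discomfort associated with bladder spasms", so the question is about timing.

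Nowhere does the plan define an analysis set, say that patients are analysed in the arm assigned, or say how a control who later receives B and O is counted.

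**The concern.** The analysis sentence names its groups by exposure rather than by arm, and neither comparator label fits the Control Group. It is not a placebo group. Under item 2 it is not reliably a no-suppository group either. An analyst who finds a control with a post-operative B and O suppository has no rule to follow. Taken literally, the sentence excludes that patient from the no-suppository side, so the patient is either dropped or counted with the B and O patients.

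Both choices depend on the outcome. Under item 2, a control receives B and O because of bladder spasm, which is what the survey measures and what drives the spasm-medication endpoint. Removing such patients leaves a comparator enriched for people without spasm and biases the comparison against early B and O. Given the aim in section A, a control treated later on demand belongs in the comparator.

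**Working it through.** **Inputs.** From section D, question 5: 40% v 20% needing spasm medication; 82 per group for power above .80; total 180; pain difference 1 point, SD 2; morphine-equivalent difference 4 mg, SD 5; about 20% rescue B and O and 60% oxybutynin in a cited prostatectomy study; and "For all comparisons, we will use 2-tailed tests with alpha=.05".

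Assumptions: 60 controls v 120 B and O patients (three equal arms, the two B and O arms combined); no dropout; every control given B and O counts as having needed spasm medication; a rescue dose does not itself change the pain or morphine score. The rescue rate in this trial is not given, so a range is used.

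**1. The plan's own figure.** With mean proportion 0.30, n = [1.96·√(2·0.30·0.70) + 0.842·√(0.20·0.80 + 0.40·0.60)]² / 0.20² = (1.270 + 0.532)² / 0.04 ≈ 81.2, so 82 per group. The plan's figure is reproduced.

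**2. Analysed as randomised.** 24/60 = 40% v 24/120 = 20%. The pooled proportion is 48/180 = 0.267. The standard error under no difference is √(0.267·0.733·(1/60 + 1/120)) = 0.0699, and under the planned rates √(0.24/60 + 0.16/120) = 0.0730. Power = Φ((0.20 − 1.96·0.0699)/0.0730) = Φ(0.86) = 0.81.

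**3. Grouped by receipt.** If k controls with spasm receive B and O and are moved, the comparison is (24 − k)/(60 − k) v (24 + k)/(120 + k). If they are dropped, the B and O side stays at 20%.

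| Controls given B and O (k) | No suppository | B and O, moved | Difference, moved | B and O, dropped |
|---|---|---|---|---|
| 0 | 24/60 = 40.0% | 24/120 = 20.0% | +20.0 points | 20.0% |
| 6 | 18/54 = 33.3% | 30/126 = 23.8% | +9.5 | 20.0% |
| 12 | 12/48 = 25.0% | 36/132 = 27.3% | −2.3 | 20.0% |
| 18 | 6/42 = 14.3% | 42/138 = 30.4% | −16.1 | 20.0% |

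The two anchors for k come from the cited study. Its 20% applied directly to 60 controls gives 12. If its 20% and 60% do not overlap, B and O is 20/80 = a quarter of spasm treatment, and a quarter of 24 is 6.

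When patients are moved, the difference is zero where (24 − k)(120 + k) = (24 + k)(60 − k). That is 1440 = 132k, so k = 10.9, or 18.2% of controls.

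**4. Chance of a significant result for B and O** (simulated, Pearson chi-squared, two-sided .05, true rates 40% v 20%).

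| Share of controls with spasm given B and O | As randomised | Moved | Dropped |
|---|---|---|---|
| A quarter (about 6) | 0.81 | 0.27 | 0.48 |
| Half (about 12) | 0.81 | 0.01 | 0.12 |

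With no true effect (40% v 40%) and half rescued, moving patients shows significant harm in 72% of simulated trials.

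**5. Pain and morphine equivalents.** Here the result depends on the correlation ρ between the tendency to receive rescue B and O and the outcome score. The documents do not give ρ. With 12 of 60 controls (20%) moved, the mean estimates are:

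| ρ | Pain (true benefit 1 point) | Morphine equivalents (true benefit 4 mg) |
|---|---|---|
| 0.3 | 0.63 | 2.9 mg |
| 0.5 | 0.43 | 2.5 mg |
| 1 | −0.05 | 1.3 mg |

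Morphine equivalents change sign (−0.7 mg) only in the extreme setting of 40% of controls moved and ρ = 1.

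**6. The other reading of the allocation (90 v 90).** As randomised, power for spasm medication is 0.84. Moving 20% of controls (18) gives 18/72 = 25.0% v 36/108 = 33.3%. The zero point is 1620 = 126k, so k = 12.9, or 14.3% of controls.

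**The case against.** A reader might infer that the plan orders regrouping by suppository received. It does not. The comparator label can be read as loose shorthand for the Control Group, whose rectal exam is there to imitate suppository placement. The sample-size text also points towards randomised groups: it contrasts treatment and control groups and expects 40% of controls to need spasm medication. It introduces that outcome with figures that include rescue B and O. This stands as evidence of intent, but it sets no rule for the analysis, and the one sentence describing the comparison uses different terms.

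Item 3 of section D is the second strong objection. If no control receives B and O, the two groupings coincide and nothing is distorted. That is correct, and it makes the size of the problem conditional. But item 2 says the opposite, so the documents do not settle whether crossover occurs.

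Third, the figure of 12 rescued controls borrows a rate from prostatectomy patients, in a study where most spasm treatment was oxybutynin. The text does not say which arm that rate came from. With 6 controls moved, the effect is about halved (9.5 of 20 points), not erased. This also stands, and it is why a range is shown.

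Finally, it would be tempting to say that the sickest controls are the ones moved. The text does not support that: item 2 requires any spasm, the patient's wish and the surgeon's agreement. The patients concerned are symptomatic controls, not necessarily the worst affected.

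**Conclusion.** The point holds as an undefined comparison whose wording fits no randomised arm and leaves room for an outcome-dependent grouping. It does not hold as a claim that the plan will move or drop rescued controls, or that the result will be reversed.

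The size is conditional. For spasm medication, with the plan's 40% v 20% and an assumed 60 v 120 split, moving 6 rescued controls reduces the 20-point difference to 9.5 points, and moving 12 turns it into −2.3 points. For pain the loss depends on an assumed correlation, and the effect is erased only towards the extreme of the range. For morphine equivalents the distortion is mainly attenuation. If no control receives B and O, the bias is zero.

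It should still be corrected before analysis. Followed literally, the stated comparison would bias an endpoint used to set the sample size, and the analysis rule should not be left until crossovers have been seen.

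**What to change.** 1. In the data-analysis paragraph of section D, replace the placebo/no suppository wording with: *the Control Group, analysed as randomised*.
2. Add: *A control patient who receives a B and O suppository post-operatively stays in the Control Group and is counted as having needed spasm medication.*
3. Report the number of controls who received B and O.
4. Reconcile items 2 and 3 of section D on whether controls may receive a suppository. The analysis rule above works whichever way the sponsor resolves this.

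The cost is two or three sentences and no new procedure. Chart review already collects post-operative antimuscarinics and pain medication; rescue B and O should be named as an item to extract.

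The one small downside is that, if controls do receive B and O, the estimate is early B and O against usual on-demand care, not against never receiving it. That is the question section A asks.

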Here, we will want to detect a 20% difference between groups. Assuming that in the treatment group, 20% of patients need rescue medication for bladder spasm, while 40% need such meds in the control group, we would need n=82 per group (total N=164) in order to detect a difference this large with power >.80.

Therefore, in order to have adequate power across all 3 outcome measures, we plan to enroll a total of 180 subjects, randomized equally across treatment and control groups.

6. Identify all drugs and devices to be used, if applicable,. If the drug or device is investigational under FDA policy, list the actual IND/IDE number and respective source, supplier, and/or sponsor. If an IND/IDE has been assigned provide the FDA

stage status. Note the proposed dosage related information including instructions for administering, adverse effects, compatibility in infusions, and stability.

Please see package inserts for B and O suprette suppositories attached to this submission. We are also including Ditropan, which is the oral anti-muscarinic to be included in this study. The dosage of B&O will be 16.2mg/30mg which is in the formulary at GW. Ditropan will be given in the normal 5 mg dosage.

7. Identify all procedures that will be used for the purpose of this research. If blood is to be drawn, indicate amount to be withdrawn per single withdrawal, and the total amount of blood to be drawn. If transfusions are anticipated, include assurance that the volume of blood removed for research purposes will not necessitate a transfusion. [Refer to Section 1.5.5]

E. Study Population –(Gender and Minority Inclusions):

1. Describe the characteristics of the subject population, include the anticipated number of normal volunteers, age ranges, sex, ethnic background, and health status.

Identify the criteria for inclusion or exclusion (especially women and/or minorities).

Explain the rationale for the use of special classes of subjects, such as fetuses, pregnant women, or others who are likely to be vulnerable, especially those whose ability to give voluntary informed consent may be questionable.

The subject population will be patients seen at GW for lithotripsy procedures. This will include men and women ages 18-89. It will include all ethnic backgrounds, and anyone who has been cleared for surgery.

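### No primary outcome, success rule or fixed contrast: three unranked outcomes in three arms are each tested at two-sided .05, so the planned result cannot be identified and the chance of a false positive can exceed the stated level

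*Combined protocol and SAP*

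**What the plan says.** Section A states a hypothesis that early B and O administration "will reduce the amount of pain medications that people will need post-operatively, reduce the amount of discomfort that patients experience from bladder spasms", and possibly shortens hospital stay. The outcomes are listed side by side and not ranked.

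Section D, item 2: "The patients will be divided into three research arms" (control, postoperative OR, preoperative OR).

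Section D, data analysis paragraph: t-tests for continuous variables and Pearson chi-squared tests for categorical ones. "Analysis will be tailored to compare B and O Supprenettes Suppositories and placebo/no suppository". It does not say whether the two B and O arms are combined or compared with control one at a time.

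Section D, question 5 (sample size) gives the only significance level: "For all comparisons, we will use 2-tailed tests with alpha=.05". It then sizes each outcome by itself at power above .80:
- morphine equivalent dose: "we would need n=26 per group, or total N=51"
- pain: "we would need 64 per group, or total N=128"
- rescue medication for spasm: "we would need n=82 per group (total N=164"

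It concludes that "in order to have adequate power across all 3 outcome measures, we plan to enroll a total of 180 subjects". No section names a primary outcome, a testing order, a rule for how many outcomes must succeed, or an adjustment for multiple tests.

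**The concern.** With three outcomes of equal standing, each tested at .05, there are several routes to a significant result and no statement of which one was planned. If the contrast is also open, the analyst can choose between three pooled tests and six arm-versus-control tests. A reader of the eventual manuscript could not tell whether a reported p-value below .05 was the intended test or the best of several. Depending on how success is judged, the chance of declaring a benefit when there is none could be a multiple of the stated level.

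**Working it through.** **1. Is an adjustment hidden in the sample sizes?** Inputs from section D, question 5: d = 4/5 = 0.8 for morphine dose, d = 1/2 = 0.5 for pain, 20% vs 40% for rescue medication, two-sided .05, power .80.

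- Means, normal approximation: n per group = 2(1.960 + 0.842)²/d². This gives 24.5 (25) for d = 0.8 and 62.8 (63) for d = 0.5. The t-based solution gives 25.5 and 63.8, which round up to the stated 26 and 64.
- Proportions: n = [1.960√(2 × 0.3 × 0.7) + 0.842√(0.2 × 0.8 + 0.4 × 0.6)]²/0.2² = (1.270 + 0.532)²/0.04 ≈ 81.2, so 82, as stated.

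Every per-group n matches an unadjusted two-group test at .05, so no correction is built in. (The total of 51 for morphine dose should be 2 × 26 = 52; this does not affect the point.)

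**2. Chance of at least one false positive when B and O has no effect.** Assumptions not in the documents: 180 split as 60 per arm, any one significant outcome counts, equal correlation between outcomes.

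- Pooled arms, independent outcomes: 1 − 0.95³ = 14.3%.
- Each arm vs control: six tests would give 1 − 0.95⁶ = 26.5% if independent, but the shared control arm lowers this to 24.8%.
- Only results favouring B and O, pooled, independent: 1 − 0.975³ = 7.3%.

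Simulation of the test statistics (1,000,000 replicates per correlation):

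| Outcome correlation | Pooled, either direction | Each arm, either direction | Pooled, favouring B and O | Each arm, favouring B and O |
|---|---|---|---|---|
| 0 | 14.2% | 24.8% | 7.3% | 13.0% |
| 0.5 | 12.5% | 21.9% | 6.3% | 11.0% |
| 0.8 | 9.8% | 17.3% | 4.9% | 8.7% |
| 0.9 | 8.4% | 14.9% | 4.2% | 7.5% |
| Single test | 5% | 5% | 2.5% | 2.5% |

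A patient-level check with 60 per arm, two t-tests and one chi-squared test (40% event rate assumed) gave 14.0%, 12.8% and 10.8% pooled, and 24.8%, 22.7% and 19.1% for each arm, at correlations 0, 0.5 and 0.8 (either direction).

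**3. Is naming a primary outcome enough?** Two unadjusted arm-versus-control tests on one outcome still give about 9% in either direction. The contrast must be fixed as well.

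**4. Power of the candidate contrasts at the plan's effect sizes.** For the t-tests, the noncentrality is d√(n₁n₂/(n₁+n₂)): d√40 at 120 vs 60 and d√30 at 60 vs 60.

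| Outcome | Pooled, both arms work | Pooled, one arm works | Pairwise 60 vs 60 | Pairwise after a significant three-group test, one arm works |
|---|---|---|---|---|
| Morphine dose (d = 0.8) | 0.999 | 0.67 | 0.99 | 0.99 |
| Pain (d = 0.5) | 0.88 | 0.33 | 0.775 | 0.73 |
| Rescue medication (20% vs 40%) | 0.81 | 0.27 | 0.68 | 0.61 |

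**The case against.** **The rule that any one outcome suffices is an assumption.** This stands. Section A joins its outcomes, and each is sized by itself. If each were reported as its own claim under the pooled contrast, each would keep its .05. If all three had to be significant, the false-positive chance would be under 2%, but pooled power for all three would be 0.999 × 0.882 × 0.813 = 0.72 at correlation 0 and could not exceed 0.81. The closing sample-size sentence about power on all three outcomes sets enrolment; it is not a success rule. The documents choose none of these readings, and that is the gap.

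**The hypothesis is directional.** This also stands. A significant result favouring control would not support it, so the one-direction columns describe false support for B and O. They are about half the two-direction figures, but the ratio to a single test is much the same.

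**The text leans towards pooling.** Largely fair. The analysis paragraph sets B and O against no suppository, and the sizing is for two groups. The 25% to 17% range therefore belongs to the less supported reading, though nothing excludes it.

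**60 per arm is not stated.** Equal randomisation across treatment and control could be read as 90 vs 90. That hardly affects the error rates; it would raise power to 0.92 for pain and 0.84 for rescue medication. Item 2's random selection among three groups makes about 60 per arm the natural reading.

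**Timing.** A reader might infer that a preoperative versus postoperative test is planned and should be counted; all pairwise tests would then give 32% to 23% (correlation 0 to 0.8). Section B does name timing as a gap, but section A does not hypothesise a difference between the two time points and the analysis paragraph names no such test. That range is therefore not the plan's error rate.

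**Conclusion.** The concern holds as an omission with a conditional size. The documents leave open the primary outcome, the success rule and the form of the contrast, while applying .05 to every comparison. Under the stated assumptions the error chance is about two to five times that of a single test for correlations of 0 to 0.8. At 0.9 it is still about 8% pooled and 15% for each arm, in either direction.

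Two stronger readings are tempting but not supported. One is that the trial has a false-positive rate of 10% to 25%: the documents give neither the outcome correlation nor a rule that one significant outcome is enough. The other is that only morphine dose can be primary because its stated 26 per group is the only one that 60 per arm satisfies. That comparison is pairwise; under the pooled contrast all three outcomes exceed 0.80 power if both arms work.

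**What to change.** Before analysis:

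1. Name one primary outcome and its time window. The choice is the sponsor's. The window needs stating because the sizing text refers to immediate postoperative dose, while the survey and chart review in section D, item 3 refer to 24 hours.
2. Fix one contrast for it. Closest to the analysis paragraph is both B and O arms combined versus control, one two-sided test at .05.
3. Report every other outcome, including length of stay, as secondary, with estimates and 95% confidence intervals and no success claim.
4. If timing is to be a planned comparison, replace the pooled test with one three-group test at .05 on the primary outcome and, only if it is significant, the three pairwise tests at .05. With three arms this is a closed procedure; simulated error was 0.050. State the pairwise power at 60 per arm.

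The cost is analysis wording, with three downsides. The remaining outcomes lose equal standing. The pooled test loses much power if only one arm works (0.67, 0.33 and 0.27 for morphine dose, pain and rescue medication). If morphine dose is primary, a rule is needed on whether opium from suppositories counts towards it.
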